14.2.2. Safety Population

The safety population, defined as all randomized subjects who receive at least 1 dose of study drug (olanzapine, samidorphan, or placebo), will be used in the safety analyses.

14.3. Demographics and Baseline Data

Demographics and baseline characteristics such as gender, age, race, ethnicity, weight, BMI will be summarized with descriptive statistics to assess the comparability of the study groups.

If there are heterogeneities between treatment groups in any of the subject characteristics that are of clinical importance or could affect the treatment outcome, the impact of the imbalances will be investigated and, if necessary, appropriate adjustments will be considered in the efficacy and safety analyses.

Medical history will be summarized for the safety population using the number of observations and percentage of subjects by body system.

14.4. Efficacy Analyses

The primary endpoint is the absolute change in PANSS total score from randomization to the end of Part A (ie, the end of the 12-week, placebo-controlled double-blind treatment period) and will be evaluated by treatment group (ALKS 3831 vs. the placebo group [olanzapine alone]) using a 2-sided mixed-model for repeated measures (MMRM) to test for equivalence at an alpha level of 0.05. The primary analysis will be conducted in the FAS 1 population. More details about this analysis will be provided in the SAP.

The secondary endpoint, percent change in weight from randomization to the end of Part A, will be evaluated by treatment group using an MMRM approach similar to that of the primary endpoint. However, this will be a superiority analysis. Each treatment group will be compared to the placebo group with a 2-sided hypothesis test to test for superiority at an alpha level of 0.05. The secondary efficacy analysis will also be conducted in the FAS 1 population. More details about this analysis will be provided in the SAP.

Analysis of other secondary endpoints and additional endpoints will include inferential analyses and descriptive analyses by visit (mean, SD, median, minimum, and maximum for continuous variables and number and percent for categorical variables), as appropriate.

Analyses for the primary and secondary endpoints will be repeated in the FAS 2 population as sensitivity analyses when applicable. Additional details regarding these analyses will be provided in the SAP.

14.5. Pharmacokinetic/Pharmacodynamic Analyses

For all subjects, plasma samples will be collected on Visits 2-23 to quantify the concentrations of olanzapine, samidorphan, and RDC-9986 (primary metabolite of samidorphan). Pharmacokinetic data may be used to assess compliance and/or included in subsequent population PK evaluation conducted outside of this study.

14.6. Safety and Tolerability Analyses

Reported AE terms will be coded using the Medical Dictionary for Regulatory Activities (MedDRA[®]) preferred terms and system organ classes. Descriptive summary statistics will be provided for AEs, laboratory tests, and vital signs and will include mean, SD, median, minimum and maximum for continuous variables and number and percent for categorical variables.

The incidence of AEs, including clinically significant abnormal laboratory tests or ECG values, will be summarized for each treatment group and overall, by severity and by relationship to study drug. The summary tables will include the number and percent of subjects with AEs overall, by

system organ class, and by preferred terms within each system organ class. AEs resulting in treatment discontinuation or modification will be identified.

Laboratory tests will be summarized by visit for the absolute value itself and for change from baseline. Tables showing the shift from baseline will also be presented.

ECG findings will be summarized by visit. Concomitant medications will be categorized and presented using the World Health Organization (WHO) drug Anatomical Therapeutic Chemical (ATC) classification system.

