8.2. Schedule of Visits and Assessments

The schedule of visits and assessments for Part A is shown in [Table 1](#). The schedule of visits and assessments for Part B is shown in [Table 2](#).

Because fasting glucose and insulin levels will be measured at some visits, subjects will be instructed not to eat or drink for 8 hours before these visits: Visit 2, Visit 3, Visit 13, and Visit 23/ET (see [Table 1](#) and [Table 2](#)). Random glucose and insulin levels will be measured at visits where glucose and insulin measurements are indicated, but fasting is not required.

For a missed visit, the site should attempt to contact the subject to reschedule.

Premature discontinuation procedures are provided in [Section 7.3](#).

Figure 1: Study Design Schematic

[figure not shown]

Table 1: Schedule of Assessments (Part A)

	Screening	Olanzapine	Double-Blind Placebo-Controlled Treatment Period										Transition ¹
	Outpatient Visits		Inpatient Stay			Outpatient Visits						Inpatient Stay ²	
Study Visit	1	2	3	4	5	6	7	8	9	10	11	12	13
Study Day	-30 to -1	1	8 (±1)	9 (±1)	10 (±1)	15 (±1)	22 (±2)	29 (±2)	36 (±2)	50 (±2)	64 (±2)	78 (±2)	92 (±2)
Study Week			1			2	3	4	5	7	9	11	13
Informed Consent	X												
Demographics, Medical/Psychiatric History	X												
Height, Weight, and Waist Circumference ³	X	X	X	X	X	X	X	X	X	X	X	X	X
Pregnancy Test ⁴	X	X											X
Drug Screens ⁵	X	X	X	X	X	X	X	X	X	X	X	X	X
Timeline Follow-Back (TLFB) ⁶	X	X								X			X
Vital Signs ⁷	X	X	X ⁸	X ⁸	X ⁸	X ⁸	X	X	X	X	X	X	X ⁸
Blood and urine samples for clinical labs ⁹	X	X	X		X	X			X		X		X
Hemoglobin A1c, C-reactive protein, leptin	X	X	X								X		X
Carbohydrate Deficient Transferrin (CDT)	X	X									X		X
Electrocardiogram (ECG) ¹⁰	X	X ¹¹	X		X	X							X
Physical Examination ¹²	X	X	X										X
Columbia Suicide Severity Rating Scale (C-SSRS) ¹³	X	X	X	X	X	X	X	X	X	X	X	X	X

	Screening	Olanzapine	Double-Blind Placebo-Controlled Treatment Period										Transition ¹
	Outpatient Visits		Inpatient Stay			Outpatient Visits						Inpatient Stay ²	
Study Visit	1	2	3	4	5	6	7	8	9	10	11	12	13
Study Day	-30 to -1	1	8 (±1)	9 (±1)	10 (±1)	15 (±1)	22 (±2)	29 (±2)	36 (±2)	50 (±2)	64 (±2)	78 (±2)	92 (±2)
Study Week			1			2	3	4	5	7	9	11	13
Positive and Negative Syndrome Scale (PANSS)	X	X	X			X	X		X		X		X
Clinical Global Impressions-Severity (CGI-S)	X	X	X			X	X		X		X		X
Eligibility Criteria Review	X	X	X										
Randomization			X										
Dispense Emergency Treatment Card					X								

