Pharmacogenetic blood sample			X										
Blood samples for PK		X	X	X	X	X	X	X	X	X	X	X	X
Personal and Social Performance Scale (PSP)		X	X							X			X
Food Craving Inventory (FCI)		X	X			X							X
Impact of Weight on Quality of Life – Lite Questionnaire (IWQOL-Lite)		X	X										X
Interactive Web Response System (IWRS)			X	X	X	X	X	X	X	X	X	X	X
Olanzapine Dosing		X	X	X	X	X	X	X	X	X	X	X	X
Double-Blind Samidorphan/ Placebo Dosing ¹⁴			X	X	X	X	X	X	X	X	X	X	
Adverse Event (AE) Monitoring	X	X	X	X	X	X	X	X	X	X	X	X	X

	Screening	Olanzapine	Double-Blind Placebo-Controlled Treatment Period										Transition ¹
	Outpatient Visits		Inpatient Stay			Outpatient Visits						Inpatient Stay ²	
Study Visit	1	2	3	4	5	6	7	8	9	10	11	12	13
Study Day	-30 to -1	1	8 (±1)	9 (±1)	10 (±1)	15 (±1)	22 (±2)	29 (±2)	36 (±2)	50 (±2)	64 (±2)	78 (±2)	92 (±2)
Study Week			1			2	3	4	5	7	9	11	13
Concomitant Medication Review	X	X	X	X	X	X	X	X	X	X	X	X	X
Clinical Validation Inventory for Study Admission (C-VISA TM)	X												

¹ Transition Visit = the end of Part A and the beginning of Part B. Assessments at this visit are included in both schedules for convenience.

² All measures should be taken pre-dose at Visit 13 except where indicated

³ Height will be measured at screening only; weight and waist circumference will be measured at all indicated visits

⁴ Serum pregnancy test at screening; urine pregnancy test at other time points

⁵ Centralized drug screen testing at screening, local drug screen testing via dipstick at other time points. The urine drug screen includes benzodiazepines, opioids, amphetamine/methamphetamine, and cocaine.

⁶ Alcohol use only

⁷ Orthostatic blood pressure and heart rate measurements will be taken anytime pre-dose and approximately 1 hour post-dose at Visits 3 - 6 and Visit 13 only. At all other dosing visits, routine vital sign assessments will be conducted anytime pre-dose. At all other visits (when no dosing occurs) assessments will be conducted anytime.

⁸ Collect pre-dose and post-dose data

⁹ An overnight fast is required for labs at Visit 2, Visit 3, and Visit 13. Thyroid stimulating hormone should be assessed at screening only.

¹⁰ ECG will be measured anytime pre-dose and approximately 3 hours post-dose except for Visit 1 and Visit 2 where only 1 ECG will be done. For Visit 2, the ECG should be completed before dosing. For Visit 6, dosing may be done earlier than normal to accommodate post-dose procedure.

¹¹ Collect data pre-dose

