8.3.11. Laboratory Assessments

Blood and urine samples for laboratory assessments will be collected according to the schedule shown in [Table 1](#) and [Table 2](#). Overnight fasting (no eating or drinking for 8 hours before the visit) will be required for labs at Visit 2, Visit 3, Visit 13, and Visit 23/ET. Otherwise, samples will be collected in accordance with the site's usual procedures and analyzed by a central laboratory. Follow-up samples may be obtained for repeat testing as clinically indicated.

Specific hematology, biochemistry, and urinalysis assessments are listed in [Table 3](#). Overnight fasting is required for some visits because fasting glucose and insulin levels (value and absolute change from baseline) will be measured. Otherwise, random glucose and insulin levels will be taken.

Table 3: Clinical Laboratory Assessments

Hematology	Biochemistry	Urinalysis

 • Hematocrit • Hemoglobin • Red blood cell count • Total and differential (absolute) white blood cell count • Platelets 	
 • Sodium • Potassium • Bicarbonate • Glucose¹ • Creatinine • Total protein • Blood urea nitrogen (BUN) • Albumin • Albumin/globulin ratio • Total bilirubin • Alanine transferase (ALT) • Aspartate transferase (AST) • Lactic dehydrogenase (LDH) • Gamma-glutamyl transferase (GGT) • Alkaline phosphatase (ALK-P) • Creatine phosphokinase (CPK) • Insulin¹ • Triglyceride • Total, HDL and LDL cholesterol • Prolactin • Thyroid stimulating hormone (TSH)² 	
 • Color • pH • Specific gravity • Ketones • Protein • Glucose¹ • Bilirubin • Nitrite • Urobilinogen • Occult blood • Cotinine • Microscopic examination of sediment, only if urinalysis dipstick results are abnormal

¹ Requires fasting where indicated on [Table 1](#) and [Table 2](#) (see also [Section 8.3.11](#))

² Assessed at screening only

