3.1.1 Baseline Definition

Baseline for Part A is defined as the last non-missing observation on or before the first dose of study drug following randomization at Visit 3 (Day 8).

Baseline for Part B is defined as the last non-missing observation on or before the date of the first dose of study drug at Visit 13 (Day 92).

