3.7.3 Clinical Laboratory Parameters

Laboratory parameters will be presented in conventional units. Only laboratory results at the scheduled visits will be included in the summary tables. All lab data will be included in the listings.

Results will be summarized for hematology and chemistry by visit and the treatment group for Part A and Part B.

Additionally, for select parameters, number and percentage of subjects with values considered potentially clinically significant (PCS) occurring at any time post-baseline will be summarized

by treatment group. Criteria for PCS are presented in Table 1 and Table 2. Criteria for shift in lipids, glucose and HbA1c are presented in Table 3 and Table 4.

Table 1: Potentially Clinically Significant Results Criteria for Chemistry

Parameters	Criteria
Albumin	<2.5 g/dL
Alkaline phosphatase (U/L)	≥3 x ULN
Alanine Aminotransferase (U/L)	≥3 x ULN
Aspartate Aminotransferase (U/L)	≥3 x ULN
Alanine Aminotransferase (U/L)	≥3 x ULN
Bilirubin, Total	≥2.0 mg/dL
Blood Urea Nitrogen	>30 mg/dL
Cholesterol, Random	>300 mg/dL
Cholesterol, Fasting	≥240 mg/dL
Cholesterol, HDL fasting	≤30 mg/dL
Cholesterol, LDL fasting	≥160 mg/dL
Creatine Kinase (U/L)	≥3 x ULN
Creatinine	≥2.0 mg/dL
Glucose, Random	<50 mg/dL or ≥200 mg/dL
Potassium	<3 mmol/L or >5.5 mmol/L
Lactate Dehydrogenase (U/L)	>3 x ULN
Phosphate	<2 mg/dl or >5 mg/dl
Prolactin (Female)	>30 ng/mL
Prolactin (Male)	>20 ng/mL
Sodium	<130 mmol/L or >150 mmol/L
Triglycerides, fasting (Female)	≥120 mg/dL
Triglycerides, fasting (Male)	≥160 mg/dL

Table 2: Potentially Clinically Significant Results Criteria for Hematology

Parameters	Criteria
Eosinophils	$>1.0 \times 10^3/\text{uL}$
Hematocrit (Female)	$\leq 32\%$
Hematocrit (Male)	$\leq 37\%$
Neutrophils, Absolute	$<1.5 \times 10^3/\text{uL}$
Platelets	$<75.0 \times 10^3 \text{ cells/uL}$ or $\geq 700.0 \times 10^3 \text{ cells/uL}$
Leukocytes	$\leq 2.8 \times 10^3/\text{uL}$ or $\geq 16.0 \times 10^3/\text{uL}$

Table 3: Shifts Category in Lipid Parameters from Baseline to Any Post-Baseline.

Total cholesterol (fasting) mg/dL
Normal (<200) to High (≥ 240)
Borderline (≥ 200 and < 240) to High (≥ 240)
Normal/Borderline (<240) to High (≥ 240)
Normal (<200) to borderline/High (≥ 200)
Increase ≥ 40 mg/dL
LDL Cholesterol (fasting) mg/dL
Normal (<100) to high (≥ 160)
Borderline (≥ 100 and < 160) to high (≥ 160)
Normal/borderline (<160) to high (>160)
Normal (< 100) to borderline/high (≥ 100)
Increase ≥ 30 mg/dL
HDL Cholesterol (fasting) mg/dL

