3.11.1.3 Early termination (ET) visit

An early termination (ET) visit can be mapped to a scheduled visit and be used for analysis and summaries only if there is no valid value already at the mapped visit.

A mapped ET visit will be treated as a scheduled visit to be included in table summaries. Otherwise, it will be treated as an unscheduled visit.

Two rules will be used to map an ET visit.

First, a 7-day (inclusive) window (\leq last dose date + 7) will be used to determine if the assessment at the ET visit is considered to be an on-treatment result. If an ET visit is within 7 days after the last dose of samidorphan/placebo, it will be considered as a valid on-treatment

visit.

Second, visit windows (inpatient stay is excluded) will be applied to determine to which visit an ET valid on-treatment assessment can be mapped to. Visit windows are defined in Table 8 below.

If a subject didn't complete the Part A, his/her ET assessment will not be mapped to Part B visits, i.e. Visit 14 to 23.

Table 8: Visit Window Definition

Analysis Visit to be Mapped to	Target Study Day	Visit Window
Visit 6	15	[9, 18]
Visit 7	22	[19, 25]
Visit 8	29	[26, 32]
Visit 9	36	[33, 43]
Visit 10	50	[44, 57]
Visit 11	64	[58, 71]
Visit 12	78	[72, 85]
Visit 13	92	[86, 98]
Visit 16	99	[99, 102]
Visit 17	106	[103, 109]
Visit 18	113	[110, 116]
Visit 19	120	[117, 127]
Visit 20	134	[128, 141]
Visit 21	148	[142, 155]
Visit 22	162	[156, 169]
Visit 23	176	[170, 183]

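### By-visit change tables for glucose, insulin and lipids have no fasting restriction, although the period baselines are fasting and 4 of 5 on-treatment visits in each period are not

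*Protocol*

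**What the plan says.** **Summary rule.** Protocol 14.6: "Laboratory tests will be summarized by visit for the absolute value itself and for change from baseline". SAP 3.7.3: "Results will be summarized for hematology and chemistry by visit and the treatment group for Part A and Part B". The SAP sentence does not mention change from baseline, but SAP 3.10 declares no departures from the protocol's analyses, so the protocol rule stands. Neither sentence refers to fasting state.

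**Baseline.** SAP 3.1.1 gives one rule for each part. For Part A: "Baseline for Part A is defined as the last non-missing observation on or before the first dose of study drug". The dose meant is the first one given once subjects are randomized, which is normally Visit 3. The Part B rule, which refers to Visit 13, reads: "Baseline for Part B is defined as the last non-missing observation on or before the date of the first dose of study drug". Neither definition depends on whether the sample was fasting.

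**Fasting state.** Under protocol 8.3.11 an overnight fast "will be required for labs at Visit 2, Visit 3, Visit 13, and Visit 23/ET". At other visits, protocol 8.2 says: "Random glucose and insulin levels will be measured at visits where glucose and insulin measurements are indicated, but fasting is not required".

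**Early termination (ET).** SAP 3.11.1.3: "A mapped ET visit will be treated as a scheduled visit to be included in table summaries". SAP Table 8 sets the visit windows.

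**Text that does separate the two states.** Protocol 8.3.11 explains the fasting visits by the need for fasting glucose and insulin, as values and as changes. Protocol 13.1 names fasting glucose and fasting insulin among the endpoints. SAP Table 1 has random and fasting rows for cholesterol. SAP Tables 3 and 4 label the lipid and glucose shifts as fasting.

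**The concern.** A by-visit change is readable as a time course only if both ends are sampled in the same state. Here the starting value is fasting and most later values are not, so a change in a table row may reflect the last meal and not drug exposure. The third study objective is the effect of samidorphan on weight and other metabolic factors, and these tables are where a reader would look for the course of glucose, insulin and lipids between the start and end of each period.

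A second route to mixing is the ET rule. Subjects who stop early give fasting samples, and these can enter the same row as random samples from subjects who continue. Dropout can differ by arm, so the mixture can too.

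**Working it through.** The plan states no figure for this point, so there is none to reproduce. The check is a visit count, a reading of the baseline rule, and an illustration on assumed values.

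**1. Visit count.** Inputs: the clinical-laboratory rows of protocol Tables 1 and 2, and the fasting visits 2, 3, 13 and 23/ET.

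| Period | Baseline | Post-baseline laboratory visits | Fasting | Random |
|---|---|---|---|---|
| Part A | 3 (fasting) | 5, 6, 9, 11, 13 | 13 | 4 of 5 |
| Part B, on treatment | 13 (fasting) | 15, 16, 19, 21, 23 | 23 | 4 of 5 |
| Part B with follow-up Visit 25 | 13 (fasting) | the above and 25 | 23 | 5 of 6 |

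Each period has one scheduled post-baseline fasting reading, or two fasting readings when its baseline is counted (3 and 13; 13 and 23).

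**2. What the baseline rule gives at a random visit.**
- *One parameter per analyte.* The Part A baseline is normally fasting Visit 3, so the change at Visits 5, 6, 9 and 11 is random minus fasting. The Part B baseline is normally fasting Visit 13, with the same result at Visits 15, 16, 19 and 21.
- *Separate fasting and random parameters.* In Part A the last scheduled random draw before the first randomized dose is Visit 1 (Day -30 to -1), since Visits 2 and 3 are fasting. Olanzapine starts on Day 1, so this change would include the lead-in week and would not be change from randomization. In Part B the rule would reach back to random Visit 11 (Day 64), which is 92 - 64 = 28 days before Part B begins.

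**3. ET mapping.** Table 8 maps an ET assessment on Days 9 to 18 to Visit 6, Days 33 to 43 to Visit 9, and Days 58 to 71 to Visit 11. All three are random laboratory visits, while the ET sample is fasting. The same table does this for Visits 16, 19 and 21 in Part B. Mapping requires that the assessment falls within 7 days of the last samidorphan or placebo dose and that the mapped visit has no valid value.

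**4. Size, on assumed values for glucose.** Take 70 placebo and 210 pooled active subjects, a true fasting change of 0 with SD 10 mg/dL, and an independent prandial component with mean *m* and SD *s*, the same in every arm. Then:
- Within-arm mean change = 0 + *m*.
- SE of the between-arm difference = sqrt(10² + *s*²) × sqrt(1/70 + 1/210), where the second factor is 0.138.
- For fasting pairs, SE = 10 × 0.138 = 1.38 mg/dL.

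| *m*, *s* (mg/dL) | Within-arm change | SE, formula | SE, simulated (2,000 runs) | Variance ratio to fasting |
|---|---|---|---|---|
| 0, 10 | 0 | 1.95 | 1.95 | 200/100 = 2 |
| 10, 15 | 10 | 2.49 | 2.46 | 325/100 = 3.25 |
| 20, 25 | 20 | 3.72 | 3.75 | 725/100 = 7.25 |
| 30, 30 | 30 | 4.36 | 4.46 | 1000/100 = 10 |

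The simulated between-arm difference stayed within 0.04 mg/dL of 0 in every row.

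**The case against.** The strongest reply is that no sentence in either document orders a fasting value to be subtracted from a random one. Protocol 14.6 is a general rule for all laboratory tests. The more specific text keeps the two states apart: protocol 8.3.11 and 13.1, and SAP Tables 1, 3 and 4. The mock tables, which might settle the matter, are in a separate document (SAP 4).

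Much of this stands. A reader might infer that the plan deliberately computes mixed changes, but the documents do not say so. What the reply does not supply is a usable rule. Both readings in step 2 give a faulty Part A change at random visits, and the one that avoids the fault (change for fasting pairs only) is not written. The SAP text does not mention insulin, and the lipid endpoint in protocol 13.1 carries no fasting qualifier.

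Three stronger readings are also tempting and do not hold:
- *The metabolic results cannot be interpreted.* The Visit 3 to 13 and Visit 13 to 23 fasting pairs are clean. HbA1c does not depend on the fasting split. Part A contrasts between randomized arms at the same random visit are unbiased if prandial state is similar across arms. The protocol measures food craving and expects weight to differ, so that similarity is not assured, but nothing in the documents shows that it fails.
- *Each period has only one fasting reading.* That is true only of scheduled post-baseline readings.
- *The gap between the protocol's random and fasting glucose exclusion limits (200 - 126 = 74 mg/dL) measures the artefact.* Those are classification cut-offs and not an estimate of random minus fasting.

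For lipids the argument rests on shared draws. The explicit statement about random sampling covers glucose and insulin, and the documents give no size for a fasting effect on any lipid.

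**Conclusion.** The point holds as a gap in the analysis rules with a predictable consequence. If protocol 14.6 and SAP 3.1.1 are applied as written, within-arm changes at 4 of 5 on-treatment visits in each period combine two sampling states, and a few rows may also take in fasting ET values. The within-arm time course is distorted by whatever the mean prandial shift is, and between-arm comparisons at those visits lose precision: 2 to 10 times the fasting variance over the assumed range. Those figures depend on the assumed shifts and SDs, on independence, and on full arms of 70 and 210. The number of ET samples affected cannot be derived from the documents.

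The importance is modest. These are descriptive safety and additional outputs, and the start-to-end fasting comparison in each period survives. The primary PANSS analysis and the weight analyses do not use these data.

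**What to change.** Add one paragraph to SAP 3.7.3, with a matching exception in 3.11.1.3:

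- Treat fasting and random glucose, insulin and lipids as separate parameters.
- Compute change from baseline, including for the glucose-to-insulin ratio, only where both samples are fasting: Visit 13 against Visit 3, and Visit 23 against Visit 13.
- Show random visits as absolute values only.
- Report fasting ET samples separately, and do not map them into random visits.

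The cost is this SAP text and the matching table shells. It needs no new data, visits or blood draws. Adding a fast at Visits 11 and 21, where blood is already drawn, would give a second post-baseline fasting point in each period. That is an optional design preference needing a protocol amendment, and it is not part of this correction.
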